## 10. DATA MANAGEMENT AND QUALITY CONTROL

## 10.1 Data Extraction and Transfer

The dialysis provider organization data warehouse teams already have processes in place to ensure that data are captured appropriately from the various originating units. DCRI will develop a module to ensure that records transmitted from the central warehouse are accurately incorporated in the study database. Pre-specified data elements will be transmitted to DCRI from the 2 dialysis provider organizations on a monthly basis. The transferred data will be cumulative – each month the information technology groups at the provider organization will generate and transfer a complete data set for overwriting the previous one. The dialysis provider IT groups will notify DCRI when each data transfer is occurring so the DCRI IT team can confirm that the transfer was successful. Standardized file formats for transmitted data will be defined during the UG3 phase in order to enable automation of extraction, transfer, and loading processes.

## 10.2 Data Quality Procedures

Primary responsibility for data quality will reside with the dialysis provider organization data warehouse teams. Data from individual dialysis units are regularly transmitted for inclusion into central data warehouses for each of the participating dialysis organizations. The data being extracted and transmitted from these central warehouses is expected to be an accurate representation of the source data collected at each dialysis unit.

## 10.3 Data Security

DCRI will use a web-based validated, electronic reporting platform. All data files being exchanged will be transferred using secure servers. During the data extraction by the dialysis providers, all personal identifiers other than dates of service and date of birth (IDs; such as medical record number, hospital account number, names) will be replaced by a unique study participant identifier. The provider organizations will manage the individual study IDs and ensure they are unique across all participants. This will be accomplished by establishing mutually exclusive ranges of values for study IDs between the two providers. In the case of relevant dates of services or procedures or dates of birth, one of the standard methods for de-identifying dates will be used, such as elapsed time from starting event versus actual starting and ending dates or age versus birth date.

For security reasons, and in compliance with regulatory guidelines, it is imperative that only the persons who own the user IDs and passwords access the system using their own unique access codes. Access codes are nontransferable. Study personnel who have not undergone training may not use the system and will not be issued user ID and password until appropriate training is completed.

## 11. STUDY RESPONSIBILITIES

## 11.1 Investigator Responsibility/Performance

By signing this protocol, DCRI and the study PI agree to be responsible for implementing and maintaining quality control and quality assurance systems to ensure that all work incidental to this protocol is conducted and data are generated, documented, and reported in compliance with the protocol; accepted standards of Good Clinical Practice (GCP); and all applicable federal, state, and local laws, rules and regulations relating to the conduct of the clinical study.

The principal investigator (PI) ensure that all personnel responsible for study conduct are provided current copies of the study protocol.

The PI will ensure that NIDDK is provided with copies of all institutional review board (IRB) actions regarding the study.

## 11.2 Training

The training of appropriate dialysis provider personnel will be the responsibility of DCRI. To ensure protocol understanding and compliance, DCRI will present a formal training session to dialysis provider personnel, to include instructions for study procedures, informed consent, and regulatory requirements.

The dialysis provider leadership are responsible for ensuring that his or her staff conduct the study according to the protocol.

## 11.3 Clinical Monitoring

DCRI will employ a "risk-based monitoring" (RBM) strategy that ensures human subject protection and data quality are held in the utmost regard. Data-Driven Trial Management (DDTM) is a targeted analysis–based surveillance effort designed to proactively minimize risk and improve quality.

DCRI focuses on a simple and pragmatic project management strategy based on the following quality by design principles with human subject protection and data quality and integrity as the foundation of project planning and execution: 1) the correct participants are consented and enrolled, 2) acceptable protocol adherence is met, 3) complete data is obtained, and 4) good clinical practices (GCP) are followed.

Integrated DCRI systems support our RBM strategies allowing us to closely monitor and track agreed upon key risk indicators and follow-up quickly with necessary interventions. Based on our significant data quality experience, the DCRI has established strategies and supporting tools to deliver high quality data that is critical for all trials including long term, event driven trials. By integrating the varied data sources and providing seamless reporting of trial data status, the study team is enabled to proactively manage trials.

As part of a concerted effort to follow the study in a detailed and orderly manner in accordance with established principles of GCP and applicable regulations, a DCRI team member will maintain frequent contact with point persons from the dialysis providers.

## 11.4 Study Documentation

Study documentation includes all electronic medical record data, the study database, sponsor-investigator correspondence, and regulatory documents (e.g., signed protocol and amendments, IRB or EC correspondence and approval, approved and signed participant consent forms, etc.).

The DCRI will prepare and maintain complete and accurate study documentation in compliance with GCP standards and applicable federal, state, and local laws, rules and regulations.

By signing the protocol, the PI acknowledges that, within legal and regulatory restrictions and institutional and ethical considerations, study documentation will be promptly and fully disclosed to NIDDK by the investigator upon request and also shall be made available at the investigator's site upon request for inspection, copying, review, and audit at reasonable times by representatives of NIDDK or responsible government agencies as required by law.

The PI agrees to promptly take any reasonable steps that are requested by NIDDK as a result of an audit to cure deficiencies in the study documentation and the study database.

## 11.5 Source Documentation

For this study, the source documentation is the electronic health record (EHR) at the dialysis providers.

## 11.6 **Protocol Deviations**

Because this is a pragmatic trial intended to evaluate effectiveness of the phosphate targets under real-world conditions, protocol deviations will be limited to: 1) enrollment of individuals who do not meet eligibility criteria or provide informed consent, and 2) breach of participant confidentiality. Deviations will be reported to DCRI and to the IRB.

## 11.7 Protocol Changes

All modifications to the protocol will be approved by the Steering Committee and submitted to the IRB for approval prior to implementation. Changes will be incorporated into the protocol as amendments. Protocol amendments and new versions of the protocol will be distributed to all HiLo personnel and partners.

## 11.8 Data Transmittal and Record Retention

The clinical data generated at the dialysis facility is retained at the data warehouse of the dialysis provider organization in accordance with each organizations standard operating procedures.

The trial database at the DCRI will be maintained for a period of 2 years following completion of the study, after which it will be archived. A copy of the data will be transferred to the NIDDK Repository in accordance with NIDDK policy. Data elements that are unique to one of the dialysis provider organizations, infrequent values, or any other elements that have potential for identifying a provider organization, dialysis facility, or participant will not be included in the repository data.

36

The DCRI will maintain the electronic trial master file and all other study-specific documentation for at least 2 years after the formal discontinuation of this study. The DCRI will notify NIDDK prior to the destruction of any study documentation. Such documentation is subject to inspection by NIDDK as well as other regulatory agencies, as provided by law.

## 11.9 Study Closeout

Upon completion of the study (defined as all participants have completed all follow-up visits, and all data transfer are complete), DCRI will notify the site of closeout. The DCRI monitor will ensure that the electronic trial master files are up-to-date and complete. DCRI will then notify the IRB of the site closures. Following the analysis of the study data and writing of the final study report/manuscript, DCRI will notify the IRB of study closure.

## 11.10 Data Sharing

A data sharing policy will be developed by the HiLo Steering Committee. The policy will be consistent with the data sharing policy of the NIDDK. Data that can potentially be linked to a specific participating dialysis provider organization will not be transmitted to NIH data repositories. This includes all data elements that are collected by only one of the two dialysis provider organizations and data categories with counts below a specified threshold. All PHI will be removed from any shared data sets including dates, ages >89 years and any other sparsely represented values that could potentially be identifying.

## 12. ETHICAL CONSIDERATIONS

By signing this protocol, the principal investigator (PI) agrees to conduct the study in compliance with the protocol, DCRI standard operating procedures and/or guidelines, International Conference on Harmonisation guidelines on Good Clinical Practice (ICH E6, the principles of which have their origin in the Declaration of Helsinki), and all other applicable federal, state, and local laws, rules, and regulations relating to the conduct of the clinical study.

## 12.1 Role of DCRI

As the study sponsor, DCRI has overall responsibility for the conduct of the study, including assurance that the study meets the regulatory requirements of the FDA. DCRI will ensure adherence to the sponsor's general responsibilities as listed in21 Code of Federal Regulations [CFR] 312.50 and other responsibilities including monitoring (21 CFR 312.56), and protocol amendments (21 CFR 312.30).

## 12.2 Informed Consent

The PI and dialysis providers have both ethical and legal responsibility to ensure that each participant being considered for inclusion in this study is given a full explanation of the study. Informed consent will be obtained from all participants before any study-related procedures are performed.

Informed consent will be documented through an electronic consent process approved by the same IRB/EC responsible for approval of this protocol. The ICF will conform to FDA regulations in 21 CFR Part 50 and to the institutional requirements for informed consent and applicable regulations.

The study details and consent process will be reviewed with the prospective study participants, and study staff will be available to answer questions regarding procedures, risks, and alternatives.

Once the appropriate essential information has been provided to the participant, and it is felt that the participant understands the implications of participating, the participant will sign and date and IRB-approved electronic consent. The participant will receive a copy of the signed ICF. The signed and dated consent will be maintained electronically as a part of the study documentation.

The participant will be informed in a timely manner through their dialysis provider if new information becomes available that may be relevant to the participant's willingness to continue participation in the trial.

## 12.3 Confidentiality of Participants

Participant confidentiality will be maintained throughout the clinical study in a way that ensures the information can always be tracked back to the source data. For this purpose, a unique participant identification (ID) code (ID number and participant name code) will be used that allows identification of all data reported for each participant.

Participant information collected in this study will comply with the standards for protection of privacy of individually identifiable health information as promulgated by HIPAA (Health Insurance Portability and Accountability Act) and as mandated in Title 45 CFR Parts 160 and 164. All records will be kept confidential, and the participant's name will not be

released at any time. Participant records will not be released to anyone other than DCRI or its designees and responsible regulatory authorities when requested. In all cases, caution will be exercised to assure the data are treated confidentially and that the participant's privacy is guaranteed.

## 12.4 Authorization for Use and Disclosure of Protected Health Information (HIPAA)

An authorization for use and disclosure of protected health information (PHI) under the HIPAA Privacy Rule (45 CFR § 164.102 *et seq*) will be obtained from every trial participant before or at the time of enrollment. It will be presented to, and signed by, the participant at the same time or prior to the electronic consent form. The dialysis provider is responsible for obtaining participants' authorizations and signatures and for explaining the elements of the HIPAA authorization form, if necessary.

HIPAA authorization will be a separate form from the electronic consent. A signed copy of the HIPAA document will be filed in the participant's medical records. Participants will be given the other signed duplicate for their personal records.

The HIPAA authorization form will contain all elements required under the HIPAA Privacy Rule. By law, IRB approval of the HIPAA authorization form for use in this study is not required, and no such approval will be sought or requested.

The dialysis provider will promptly inform DCRI of any restrictions on the use or disclosure of PHI of any participant to which the dialysis provider has agreed under the Privacy Rule. The dialysis provider will also promptly inform DCRI of any written revocation of any participant's HIPAA authorization.

## 12.5 Institutional Review Board Review

The appropriate IRB/EC must approve the protocol and informed consent documents, agree to monitor the conduct of the study, and agree to review study progress periodically, at intervals not to exceed 1 year. DCRI will ensure that the IRB/EC has approved the study *before* the study may begin.

In addition, the investigator must provide the following documentation to NIDDK:

- 1. IRB/EC annual re-approval of the protocol, per current Title 21 CFR 312.66 regulations and 1997 International Conference on Harmonisation guidelines.
- 2. IRB/EC approval of revisions to the informed consent documents or any amendments to the protocol. Any revisions to the protocol that may increase participant risk exposure must be approved before implementation. Administrative changes (such as a change in address or phone number) must be sent to IRBs/ECs but do not require their approval.

The Duke University Institutional Review Board will serve as the IRB of record for the HiLo Trial and provide regulatory oversight for the trial activities at the dialysis facilities and DCRI. Authorization agreements between the Duke IRB and the dialysis provider organizations will be established.

## 12.6 Financial Disclosure/ Conflict of Interest

Financial and other competing interests for the investigators are documented, provided to the IRB, updated annually, and maintained at DCRI.

1. STUDY DETAILS

1.1 Study Objectives

The primary objective of HiLo will be to test the primary and secondary study hypotheses:

Primary hypothesis: Compared to the current standard approach of targeting serum phosphate levels of <5.5 mg/dl, less stringent control of serum phosphate to target levels ≥ 6.5 mg/dl will improve time to all-cause mortality and number of hospitalizations. This hypothesis will be tested using a hierarchical endpoint that prioritizes improvements in all-cause mortality over hospitalizations.

Secondary hypotheses: The trial will test the secondary hypotheses that less stringent control of serum phosphate will result in increased time to death; lower per-person year (PPY) hospitalization rates; and increased serum albumin and protein catabolic rate (PCR), as markers of diet and nutrition.

1.2 Study Design

HiLo is a pragmatic, multicenter, open-label trial that will compare the effects on hospitalization, mortality, diet, and nutrition of two different phosphate management strategies in 4400 patients being treated with maintenance hemodialysis at 100-150 facilities. HiLo will randomize participants to either liberal control of serum phosphate, targeting \geq 6.5 mg/dl (Hi treatment arm, which is the new intervention to be tested), or strict control of serum phosphate, targeting <5.5 mg/dl (Lo treatment arm, which is the current standard of care).

1.3 Number of Patients

Sample size calculations

A simulation was performed in order to determine whether a sample size of 3800 provides sufficient power to reject the null hypothesis of no difference between the treatment arms in time to all cause death and number of hospitalizations.

The simulation population was created under the following parameters:

- 1:1 randomization
- For each participant, administrative censoring occurs uniformly randomly between 2 to 4 years
- Annual loss to follow up rate of 5% (for example, due to kidney transplantation, change in dialysis modality, withdrawal due to participant choice, etc.)
- Annual mortality rate of 15% in the Lo treatment arm vs. 12.8% in the Hi treatment arm.
- An average of 35% of the study population are not susceptible to hospitalization and have no chance of experiencing a hospitalization during the course of the study (zero-inflated distribution of hospitalization)
- The remaining susceptible population experiences an average a 2 hospitalizations per year in the Lo treatment arm vs. an average of 1.89 in the Hi treatment arm.

The above population was simulated across 1000 iterations. The simulated population and outcomes were analyzed using the methods described in protocol section 4.5.1. Power was estimated as the number of iterations with a p-value less than 0.05 divided by the total number of iterations.

The estimated power from the simulation indicate that a sample size of 3800 patients will have more than 95% power.

1.4 Data Sources

The primary source of data for the HiLo study will be electronic health record data received from the dialysis provider partners of the study. Dialysis providers routinely collect data on their patients in their electronic health record in the process of care, and they will share the data necessary to perform the analyses specified in this document.

Among the study population that are Medicare beneficiaries, cause-specific hospitalization data will be collected from the Centers for Medicare & Medicaid Services (CMS) Virtual Research Data Center.

2. ANALYSIS POPULATIONS

2.1 Definition of Analysis Populations

2.1.1 Intention-To-Treat (ITT) Population

The ITT population will include all patients that have consented to participation in the study. The treatment arms in analyses in the ITT population will be the participant's assigned phosphate target arm, regardless of the participant's actual phosphate levels throughout the course of the trial. The ITT population will be used in the primary analysis of efficacy and all major secondary analyses.

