## 5.3 Participant Enrollment

Since HiLo includes a phosphate target that differs from current practice guidelines, the greater-than-minimal-risk research requires individual-level consent. HiLo initially used a cluster-randomized design in which participating dialysis centers were randomized to either the intervention or control arm. After completing enrollment in 30 dialysis units (14 Hi and 16 Lo sites), there was concern for biased enrollment. Therefore, the remainder of the trial will utilize individual-level randomization to ensure that arm assignment does not influence patients' willingness to participate. Patients enrolled in the cluster-randomized design will remain in the study through completion. For the individual randomized phase, the HiLo study will randomize approximately 3,800 additional participants (1,900 per arm).

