4.5.3 Additional Analyses

An adjusted analysis of the main secondary endpoints will be performed. The following adjustment variables will be included in the models:

- Age
- Sex
- Race
- Calculated BMI
- Cause of end-stage renal disease
- Vascular access type

The covariance structure for the model will be selected in the same manner as for the serum albumin and PCR analyses described in section 4.5.2.

An adjusted analysis of time to all-cause death will be performed by repeating the analysis of the endpoint described in section 4.5.2, but including the same adjustment variables listed for the adjusted analysis of the primary endpoint in the Cox model.

Similarly, the analyses for the serum albumin and PCR will be repeated including the same adjustment variables in their respective models.

The ratio of hospitalized days will be tested with the following hypotheses:

 $H_0: \mu_H = \mu_L vs. H_1: \mu_H \neq \mu_L$

Where μ_H and μ_L are the mean ratio of hospitalized days in the Hi and Lo treatment arms respectively. If the two-sided 95% confidence interval for the difference in the mean ratios does not include 0, then the null hypothesis will be rejected.

Under a previous HiLo protocol, cluster randomization at the site level occurred but otherwise participants were enrolled and participated in the study in a similar manner to the current protocol. If it is determined to be appropriate, the primary outcomes of the participants enrolled under the cluster randomization will be analyzed separately. Furthermore, the results of this analysis will be combined with the primary analysis detailed in this SAP using meta-analysis methods. Details of both the analysis of the cluster randomized data and the meta-analysis will be provided in a future version of this document.

Additional analyses concerning COVID-19

Additional analyses are planned to investigate and control for the potential effect of the COVID-19 outbreak on the other planned analyses. If the data are available to construct an endpoint as described in section 3.3, then the primary and secondary analyses will be repeated using only non-COVID-19 related deaths and hospitalizations as endpoint events. Patients experiencing a death attributed to COVID-19 will be censored at the time of death.

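### SAP 2.1.1 puts every consented patient in the primary ITT set, which takes in about 600 facility-randomized patients whom SAP 4.5.3 and the 3,800 sizing treat as outside it

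*SAP*

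**What the plan says.** - SAP 2.1.1: "The ITT population will include all patients that have consented to participation in the study". Patients are analyzed by assigned target arm, and this set serves the primary efficacy analysis and all major secondary analyses.
- SAP 1.2 describes a comparison "in 4400 patients being treated with maintenance hemodialysis". SAP 1.3 asks "whether a sample size of 3800 provides sufficient power", and Protocol 8.1 also simulates 3,800.
- Protocol 5.3: "After completing enrollment in 30 dialysis units (14 Hi and 16 Lo sites), there was concern for biased enrollment". The trial then moved to individual randomization of roughly 3,800 further participants, 1,900 per arm. As for those already enrolled: "Patients enrolled in the cluster-randomized design will remain in the study through completion".
- SAP 4.5.3: if this is judged appropriate, "the primary outcomes of the participants enrolled under the cluster randomization will be analyzed separately", and "the results of this analysis will be combined with the primary analysis detailed in this SAP using meta-analysis methods". It adds: "Details of both the analysis of the cluster randomized data and the meta-analysis will be provided in a future version of this document".
- Protocol 8.2 defines the ITT sample by randomization rather than consent. SAP 6 declares no departure from the protocol.

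**The concern.** Cluster-phase patients consented and remain in the study, so the sentence that defines the primary set includes them. SAP 4.5.3 combines their separate result with the primary analysis, which presupposes that they are not already in it. No sentence in either document excludes them.

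Three things follow.

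- If 2.1.1 is applied as written, any selective enrollment in the facility-randomized phase enters the primary test. The variance in SAP 4.5.1 treats every patient as individually assigned and has no facility term.
- If 2.1.1 and 4.5.3 are both applied, the optional meta-analysis counts these patients twice.
- Until the text is settled, an open-label trial has two readable primary sets, about 4,400 and about 3,800, and the choice could be made after results by arm are known.

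Consent and randomization also differ as criteria. Protocol 4.5 randomizes after consent, so 2.1.1 formally takes in anyone who consented but was never assigned.

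**Working it through.** **1. Head count.** The study total is about 4,400 (SAP 1.2, Protocol synopsis) and the individual phase about 3,800 (Protocol 5.3). 4,400 - 3,800 = about 600; 600/4,400 = 13.6%; 600/30 = about 20 per facility. The 600 is printed nowhere; it is the difference of two approximate totals.

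**2. The texts side by side.**

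| Place | Cluster-phase patients in the primary set? |
|---|---|
| SAP 2.1.1 | Yes, if read literally |
| Protocol 8.2 | Undecided: they were assigned, but through their facility |
| SAP 4.5.3 | No, by implication, and conditionally |
| SAP 1.3, Protocol 8.1 (N = 3,800) | No, by implication |

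**3. The plan's own figure.** Both documents state power above 95% at 3,800. Simulating the SAP 4.5.1 test with independent patients gives 99% on Protocol 8.1 inputs (hazard ratio 0.85; 1.53 vs 1.8 hospitalizations a year), so that figure is reproduced. SAP 1.3 inputs (12.8 vs 15% mortality; 1.89 vs 2 hospitalizations) give 87%. That gap is a separate matter.

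**4. Type I error if the sets are pooled.** The test is T/V^0.5 with V = [p(N-p)/(N(N-1))] ΣU², two-sided 0.05.

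- From the documents: censoring uniform over 2-4 years, 5% annual loss, 15% annual mortality, 35% never hospitalized, 1.8 hospitalizations a year in the rest.
- Assumed: 100 individually randomized sites of 38; 30 facilities of 20 (14 Hi, 16 Lo); Poisson hospitalizations; a lognormal site effect shared by death and hospitalization, SD 0 / 0.2 / 0.3 / 0.4.
- 8,000 null trials per setting (SE 0.2-0.4 points).

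| Score ICC | 3,800 alone | 4,400 pooled |
|---|---|---|
| 0 | 4.7% | 4.7% |
| 0.03 | 4.8% | 5.4% |
| 0.06 | 4.5% | 6.6% |
| 0.09 | 3.8% | 6.3% |

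Design-effect check: variance inflation = [3800 + 600(1 + 19 × ICC)]/4400. At ICC 0.05 this is (3800 + 600 × 1.95)/4400 = 1.130, and 2(1 - Φ(1.96/√1.130)) = 6.5%. At ICC 0.10 it gives 8.1%.

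Now let Hi-facility enrollees carry lower risk of both events, at ICC 0.03:

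- 10% lower: 7.3%.
- 20% lower: 11.9%, of which 11.5 points favor Hi. With no site variation it is 12.7%, so the bias drives the error rather than the clustering.
- Sensitivity of the 20% case (4,000 trials each, SE 0.5): 12.9% at 2 hospitalizations a year; 13.2% if cluster-phase patients are followed for 3.5-4 years. A separate run of 1,000 trials gave 12.9% (SE 1.1).

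Hand check of the 20% case: 14 × 20 = 280 Hi cluster patients. The mean Hi hazard is (1900 + 280 × 0.8)/2180 = 0.974 of Lo with no true effect.

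**5. Power if the bias runs the other way** (25% higher risk in Hi-facility enrollees; ICC 0.03; 5,000 trials, SE 0.1-0.7).

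| Set | SAP 1.3 inputs | Protocol 8.1 inputs |
|---|---|---|
| Pooled, unbiased | 89.7% | 99.3% |
| 3,800 alone | 86.0% | 98.8% |
| Pooled, biased | 69.7% | 95.6% |

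Against the 3,800 alone, the biased pool loses 86.0 - 69.7 = 16.3 points or 98.8 - 95.6 = 3.2 points. Against an unbiased pool it loses 20.0 or 3.7.

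**6. Double counting.** This arises only if both rules are followed. Combine a 4,400 estimate with a 600 estimate by inverse variance, with information proportional to patients. True variance is proportional to 3800 + 4 × 600 = 6200, nominal to 5000, ratio 1.24. 2(1 - Φ(1.96/√1.24)) = 7.8% for a nominal 5% meta-analysis.

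**7. Interim base.** SAP 4.1.1 triggers at 2,000 to 2,400 enrolled, described as about half. That is 45-55% of 4,400 or 53-63% of 3,800. It fits 4,400 better, but no base is named.

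**The case against.** The best reply is that the intent is plain. SAP 4.5.3 assigns these patients to an earlier protocol, analyzes them apart and only then combines results. Its condition governs whether that separate analysis is done, not whether they join the primary test. Both sizings match the individual phase. Protocol 8.2 can be read as covering individually randomized patients only, and SAP 6 suggests reading 2.1.1 in line with it. On this view one unqualified sentence needs a clarification and no more.

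Much of this is fair as to intent. It does not repair the definition: 4.5.3 sits among the additional analyses and excludes only by implication. If the separate analysis is judged inappropriate, nothing says where these patients go. The promised SAP version covers the cluster analysis and the meta-analysis, not 2.1.1.

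Several objections on size stand. The bias figures rest on assumed shifts, and clustering alone adds little. The relevant power comparison for the fix is with the 3,800 alone (16.3 or 3.2 points), not with an unbiased pool. Double counting touches only an optional analysis. The interim trigger is an enrollment count, and no error in it is shown; a separate interim plan, not available here, may settle it. SAP 4.4.1 still describes targets as assigned to sites, so 2.1.1 may be a remnant of the cluster design, but that is a guess.

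**Conclusion.** The concern holds: SAP 2.1.1 is wrong as written. It places about 600 facility-randomized patients, 13.6% of the total, in a primary set from which the rest of the plan implies they are absent. That conclusion comes from the text and needs no assumption.

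The consequences do rest on assumptions. With no bias, type I error stays below 7% in the simulated settings. With a 20% risk difference in the Hi facilities it is about 12%, nearly all in favor of Hi. With the opposite bias, the power loss depends strongly on which document's inputs are used. The case for correcting it does not depend on these sizes: the protocol abandoned cluster randomization over concern about enrollment bias, and the primary set should be fixed before any comparison by arm.

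**What to change.** - In SAP 2.1.1 and Protocol 8.2, define the primary ITT set as all individually randomized participants (about 3,800), analyzed by assigned arm. State that participants enrolled under the cluster-randomized protocol are not in it.
- Name that set as the base and the analysis set of the interim analysis in SAP 4.1.1 and 4.7, and carry it into the separate interim plan. Half of 3,800 is 1,900, so the 2,000 to 2,400 range must be confirmed or restated.
- Use the facility-randomized patients only in the SAP 4.5.3 supplementary analysis, with inference that respects facility assignment, set out in the SAP version already promised. Record before any comparison by arm whether that analysis will be done.

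The cost is wording in two documents plus the interim plan; no new data are needed. If the cluster phase was in fact unbiased, leaving it out costs 89.7 - 86.0 = 3.7 power points under SAP 1.3 inputs and 99.3 - 98.8 = 0.5 under Protocol 8.1 inputs, partly recovered by the meta-analysis.
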